**Figure 2.1-1: Study Design Schema**

Tumor progression or response endpoints will be assessed using Response Evaluation Criteria In Solid Tumors (RECIST 1.1) criteria. Treatment with study medication will continue until RECIST 1.1 defined progression, unacceptable toxicity, or withdrawal of consent. Dose reductions will not be allowed for nivolumab or ipilimumab or ipilimumab-placebo. Treatment beyond initial

investigator-assessed progression (either clinical or radiographical) is permitted for nivolumab and ipilimumab or ipilimumab-placebo if the subject has an investigator-assessed clinical benefit and is tolerating study drug. The primary analysis of ORR for each of the platinum eligible and platinum refractory subgroups will be conducted after the last randomized subject in that subgroup has been followed for at least 6 months. Survival follow-up may continue for up to 5 years from the time of this analysis. The study will end once survival follow-up has concluded.

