A Data Monitoring Committee (DMC) will be established and meet regularly during the study to ensure that subject safety is carefully monitored and to provide oversight regarding safety and efficacy considerations in protocol CA209714, see [Section 7](#).

The analysis of ORR for each of the platinum eligible and platinum refractory subgroups will be conducted after the sufficient number of randomized subjects in the subgroup have been followed for at least 9 months. Survival follow-up may continue for up to 5 years from the time of this analysis. The study will end once survival follow-up has concluded.

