Tumor progression or response endpoints will be assessed using Response Evaluation Criteria In Solid Tumors (RECIST 1.1) criteria. Treatment with study medication will continue until RECIST 1.1 defined progression, unacceptable toxicity, 24 months of treatment, or withdrawal of consent. See [Section 3.6](#) for full details of discontinuation of study drug treatment.

Dose reductions will not be allowed for nivolumab, ipilimumab, or ipilimumab-placebo. Treatment beyond initial investigator-assessed progression (either clinical or radiographical) is permitted for nivolumab and ipilimumab or ipilimumab-placebo up to a maximum of 24 months from date of first dose if the subject has an investigator-assessed clinical benefit and is tolerating study drug (see [Section 4.5.6.1](#)).

A Data Monitoring Committee (DMC) will be established and meet regularly during the study to ensure that subject safety is carefully monitored and to provide oversight regarding safety and efficacy considerations in protocol CA209714, see [Section 7](#).

The ORR analyses for each of the platinum eligible and platinum refractory subgroups will be conducted when the sufficient number of randomized subjects in that subgroup have been followed at least 9 months. The accrual duration will be approximately 13 months. Survival follow-up may continue for up to 5 years from the time of this analysis. The study will end once survival follow-up has concluded.

The study design schematic is presented in [Figure 3.2-1](#).

This study will consist of three phases: screening, treatment, and follow-up.

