## 8.3 Endpoints

### 8.3.1 Primary Endpoint(s)

The primary objective in the study will be measured by the primary endpoint of ORR in Platinum Refractory subgroup. ORR is defined as the number of subjects with a best overall response (BOR) of a complete response (CR) or partial response (PR) divided by the number of randomized subjects for each treatment group. The BOR is defined as the best response designation, as determined by BICR, recorded between the date of randomization and the date of progression, as

assessed by BICR per RECIST 1.1 or the date of subsequent anticancer therapy (including tumor-directed radiotherapy and tumor-directed surgery), whichever occurs first. For subjects without evidence of RECIST 1.1 progression or subsequent anticancer therapy, all available response designations will contribute to the BOR assessment. For subjects who continue treatment beyond progression, the BOR will be determined based on response designations up to the time of initial RECIST 1.1 progression.

ORR will be further characterized by Duration of Response (DOR) and Time to Response (TTR). DOR is defined as the time between the date of first confirmed response to the date of the first documented tumor progression (per RECIST 1.1), or death due to any cause, whichever occurs first. Subjects who neither progress nor die will be censored on the date of their last evaluable tumor assessment. Subjects who started any subsequent anti-cancer therapy without a prior reported progression will be censored at the last evaluable tumor assessment prior to or on initiation of the subsequent anti-cancer therapy. TTR is defined as the time from randomization to the date of the first confirmed CR or PR. DOR and TTR will be evaluated for responders (confirmed CR or PR) only.

The final analysis of the primary endpoint will occur at least 9 months after the last subject in the platinum refractory subgroup has been randomized.

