### **8.3.2 Secondary Endpoint(s)**

The secondary endpoint of ORR and DOR in platinum eligible subgroup is defined similarly as described for the primary endpoint.

The BICR-assessed PFS is defined as the time from randomization to the date of first documented disease progression, as assessed by the BICR using RECIST 1.1 criteria, or death due to any cause, whichever occurs first. Subjects who died without a reported progression will be considered to have progressed on the date of their death. Subjects who did not progress or die will be censored on the date of their last evaluable tumor assessment. Subjects who did not have any on study tumor assessments and did not die will be censored on the date they were randomized. Subjects who started any subsequent anti-cancer therapy, including tumor-directed radiotherapy and tumor-directed surgery, without a prior reported progression will be censored at the last evaluable tumor assessment prior to/on initiation of the subsequent anti-cancer therapy.

OS is defined as the time between the date of randomization and the date of death. For subjects without documentation of death, OS will be censored on the last date the subject was known to be alive.

PD-L1 expression is defined as the percent of tumor cell membrane staining in a minimum of 100 evaluable tumor cells per validated Dako PD-L1 IHC assay.

The final analysis of the ORR in each of platinum eligible and platinum refractory subgroups will occur at least 9 months after the sufficient number of subjects in that subgroup have been randomized (approximately 180 in platinum eligible and 216 in platinum refractory subgroups). Analysis of the PFS and OS will also be performed at the same time as the ORR analysis.

[REDACTED]

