## 2.4 Protocol Amendments

This SAP (version3.0) incorporates the following amendments:

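### SAP 2.1 allows the final ORR analysis at 6 months' minimum follow-up, while the protocol requires at least 9 months

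*SAP*

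**What the plan says.** SAP 2.1, in the text under Figure 2.1-1, says the primary ORR analysis for each of the two subgroups "will be conducted after the last randomized subject in that subgroup has been followed for at least 6 months".

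The protocol times the same analysis in four places:

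- Synopsis, Study Design: after "the sufficient number of randomized subjects in the subgroup have been followed for at least 9 months".
- Section 3.2: when "the sufficient number of randomized subjects in that subgroup have been followed at least 9 months".
- Section 8.3.1, for the primary endpoint: the final analysis "will occur at least 9 months after the last subject in the platinum refractory subgroup has been randomized".
- Section 8.3.2, for both subgroups: the final ORR analysis "will occur at least 9 months after the sufficient number of subjects in that subgroup have been randomized", with that number given as approximately 180 platinum eligible and 216 platinum refractory. It adds: "Analysis of the PFS and OS will also be performed at the same time as the ORR analysis".

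SAP 2.4 opens with "This SAP (version3.0) incorporates the following amendments". Its table includes Revised Protocol 04 and lists clarification of interim and final analysis timing among that revision's changes. SAP 5, 7.5.1.1 and 7.5.6 give the interim trigger only (about 70% of platinum refractory subjects with 6 months). No visible SAP text gives 9 months for the final analysis.

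**The concern.** The trigger for the final analysis should leave no choice of date. Here the two governing documents set different floors for it. SAP 5 says that only the primary endpoint is tested, so the sentence governs the one confirmatory comparison, and protocol 8.3.2 ties PFS and OS to the same cut.

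Three things are at stake:

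- **Compliance.** A team working from the SAP could cut the data up to 3 months before the protocol allows.
- **Maturity.** Response must be confirmed (SAP 4.1.1), so late-enrolled subjects would have fewer scans in which a response can be seen and confirmed.
- **Discretion.** The sponsor stays blinded only until the planned interim (protocol 4.6, SAP 2.3). An open window for the final cut is better closed before then. Nothing in the documents suggests that it would be misused.

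**Working it through.** **1. Do the passages describe the same analysis?** SAP 2.1 covers both subgroups and counts from the last randomized subject. The interim covers about 70% of platinum refractory subjects, so SAP 2.1 is not an interim rule. SAP 2.1 also says that survival follow-up may run up to 5 years from this analysis. The Synopsis and protocol 3.2 attach the same statement to their 9-month analysis, so the event is the same.

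**2. Anchors.**

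| Source | Subgroup | Minimum | Counted from |
|---|---|---|---|
| SAP 2.1 | each | 6 months | last randomized subject |
| Protocol 8.3.1 | refractory | 9 months | last randomized subject |
| Synopsis, 3.2, 8.3.2 | each | 9 months | a sufficient number (8.3.2: about 180 / 216) |

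For platinum refractory, SAP 2.1 and protocol 8.3.1 share an anchor and differ by 9 - 6 = 3 months, so a cut in between breaches 8.3.1. For platinum eligible, no protocol passage uses the last subject. If more than about 180 were randomized, the protocol's 9 months could be complete while the last subject has less.

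**3. Power and alpha.** Inputs from SAP 5: 144 and 72 subjects, ORR 35% and 15%, two-sided 0.050. A Wald test on the log odds ratio gives:

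- ln(3.051) = 1.1156
- SE = sqrt[1/(144 x 0.35 x 0.65) + 1/(72 x 0.15 x 0.85)] = 0.3734
- Power = Phi(1.1156/0.3734 - 1.960) = 84.8%, against the stated 84%

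Lan-DeMets O'Brien-Fleming at 70% information gives 0.0148 and 0.0455, against the stated 0.015 and 0.045. Minimum follow-up enters none of these calculations.

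**4. Scans for the last-enrolled subject.** Inputs: 30.4375 days per month (SAP 8) and six-weekly scans to week 48 (SAP 4.1.1), taken on the nominal schedule.

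- 6 x 30.4375 / 7 = 26.1 weeks: scans at weeks 6, 12, 18, 24, so 4 scans. The latest first response confirmable at the next scan is week 18.
- 9 x 30.4375 / 7 = 39.1 weeks: scans at weeks 6 to 36, so 6 scans. The latest is week 30.

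The counts are the same if the first dose is 3 days after randomization.

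**5. Illustrative effect on ORR.** These are assumptions:

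- Uniform platinum refractory accrual over 13 months. Protocol 3.2 says "The accrual duration will be approximately 13 months", for the whole study.
- Lognormal time to response with median 2 to 4 months (the range protocol 3.2.1 gives across tumor types) and log-SD 0.4 to 0.6.
- The same timing in both arms, and eventual ORR of 35% and 15%.
- Each response is dated to the next scan and confirmed at the scan after that.

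With F the lognormal distribution function, w(k) the k-th scan time and M the minimum follow-up in months, the share of eventual responders counted at the cut is

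S(M) = sum over k of [F(w(k)) - F(w(k-1))] x P(k),

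where P(k) = (M + 13 - w(k+1)) / 13, limited to the range 0 to 1.

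| Median, log-SD | S(6) | S(9) | Combination-arm loss, 35 x [S(9) - S(6)] | Difference loss, 20 x [S(9) - S(6)] |
|---|---|---|---|---|
| 2 months, 0.4 | 99.69% | 99.99% | 0.11 points | 0.06 points |
| 4 months, 0.6 | 87.60% | 94.82% | 2.53 points | 1.44 points |

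These rows are the ends of the range. With accrual of 10 to 16 months the combination-arm loss is 0.09 to 3.13 points. Dating each response to the nearest scan instead gives 0.04 to 1.99 points at 13 months, but that can date a response before it occurs.

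**6. Landmark output.** SAP 7.5.4.1 lists a 9-month OS rate but produces a rate only if minimum follow-up has reached that time. SAP 7.5.4.4 measures minimum follow-up from the last patient's randomization to the cutoff. At a 6-month minimum the 9-month rate is not produced. At 9 months it can be.

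**The case against.** The strongest reply is that nothing need go wrong. A floor of at least 6 months does not prevent waiting 9, and a cut 9 months after the last subject satisfies both documents. The sentence sits in a study-description recap that also omits the 24-month treatment limit found in the parallel protocol text, so it looks like text that was not updated rather than a chosen earlier cut. PFS and OS are not tested, and the minimum-follow-up rule stops immature landmark rates from being reported. All of this stands and limits the seriousness. It does not remove the contradiction, because the visible SAP gives no other trigger for the final analysis. Some SAP text before Section 2 is redacted, so only the visible text can be judged. The SAP dates Revised Protocol 04 as 16-May-2018 and the protocol as 25-May-2018. Whether that explains the leftover 6 months cannot be told.

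A reader might infer more than the documents support:

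- **That the SAP forces an early cut, or that power or alpha is damaged.** It only permits an early cut, and follow-up is not an input to either figure.
- **That duration of response becomes clearly less precise.** An illustrative simulation (50 responders, exponential duration, true 6-month proportion 60 to 75%, log-SD 0.5, same accrual) gave standard deviations of the 6-month Kaplan-Meier estimate of 0.060 to 0.077 at the 6-month floor and 0.061 to 0.074 at 9 months. Means differed by at most 0.003. That does not support a precision argument.
- **That even at 9 months a last-enrolled subject could show a 6-month duration only if response was seen at week 6.** The scan windows defeat this. Under the SAP 8 duration rule, a week-12 scan done at week 11 and a week-36 scan done at week 37 give (26 x 7 + 1) / 30.4375 = 6.01 months.

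**Conclusion.** SAP 2.1 is wrong as written against the protocol revision it says it incorporates, and the numerical impact is limited. The breach is certain for platinum refractory subjects, where protocol 8.3.1 uses the same anchor with 9 months. It is not certain for platinum eligible subjects, because the protocol counts from a sufficient number randomized. There the anchor needs reconciling as well as the duration.

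The scan counts rest only on the nominal schedule. The ORR losses, about 0.1 to 2.5 points in the combination arm and 0.1 to 1.4 points in the difference, rest on assumed accrual and response timing. They show scale and do not predict a result. The finding itself rests on the text.

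**What to change.** - In SAP 2.1, replace 6 months with 9 months and keep the SAP's last-randomized-subject anchor. For platinum refractory this matches protocol 8.3.1.
- For platinum eligible, either state that this anchor is equal to or stricter than the sufficient-number wording of protocol 8.3.2, or align the anchor with 8.3.2.
- Refer to this trigger in SAP 7.5.1.1 and 7.5.2, so that the analysis sections carry the final timing as well as the interim timing.
- Preferably make the change before the interim is unblinded.

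The cost is one sentence, an anchor statement and two cross-references. Sample size, alpha, procedures and patient burden do not change. The final cut moves up to 3 months later only if the 6-month floor had been planned on.

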## 2.2 Treatment Assignment

After the subject's initial eligibility is established and informed consent has been obtained, the subject must be enrolled into the study by calling an interactive voice response system (IVRS) to obtain the subject number.

Once enrolled in the IVRS, subjects that have met all eligibility criteria will be ready to be randomized through the IVRS in a 2:1 ratio, with twice as many subjects receiving nivolumab and ipilimumab as nivolumab and ipilimumab-placebo:

- Arm A: Nivo 3 mg/kg Q2W + Ipi 1 mg/kg Q6W
- Arm B: Nivo 3 mg/kg Q2W + Ipi Placebo Q6W

The stratification factors are:

- Platinum refractory subgroup (yes vs no).
- PD-L1 status (expressing vs non-expressing or non-evaluable or indeterminate). PD-L1 status is set to expressing when tumor cell PD-L1 expression  $\geq 1\%$ . (up to 20% of randomized subjects can be included into the study as non-evaluable or indeterminate).
- HPV p-16 status (oropharyngeal Cancer HPV Positive (including unknow primary with HPV p16 positive) vs oropharyngeal Cancer HPV Negative /non-oropharyngeal Cancer).

The randomization procedures will be carried out via permuted blocks within each stratum. The exact procedures for using the IVRS will be detailed in the IVRS manual.

## 2.3 Blinding and Unblinding

The Sponsor, subjects, investigator and site staff will be blinded to the study drug administered. Each investigative site must assign an unblinded pharmacist/designee, and an unblinded site monitor will be assigned by the sponsor to provide oversight of drug supply and other unblinded study documentation.

Before breaking the blind of an individual subject's treatment during the blinded portion of the study, the investigator should determine that the unblinded information is necessary, ie, that it will alter the subject's immediate management. The Principal Investigator should only call for emergency unblinding during the blinded portion of the study AFTER the decision to discontinue the subject has been made.

[figure not shown]
The Sponsor will remain blinded until the time of the planned interim analysis of the primary endpoint.

For this study, the method of unblinding is through the Interactive Response Technology (IRT).

## 2.4 Protocol Amendments

This SAP (version3.0) incorporates the following amendments:

**Table 2.4-1: Protocol Amendments**

| Amendment   | Date of Issue | Summary of Major Changes  |
|---|---------------|---|
| Revised Protocol 01
(Incorporate Amendment 01) | 19-Jul-2016   | 
This amendment is updating the Protocol to reduce some of the burden on subjects and investigators, ensure consistency with the most current version of the nivolumab Investigator Brochure (v15) and the nivolumab label, and provide clarification of definitions and minor corrections. The major changes are as follows:
 
 
• Change the title and contact information of the medical monitor.
 
• Change on the biomarkers collection schedule
 
• PK and IMG Follow up visit samples no longer required to be collected.
 
• Updated Algorithms for Renal, Pulmonary, Hepatic and Skin to match with updated Nivolumab IB v15. (includes correction identified in nivo IB v15 erratum)
 
 |
| Revised Protocol 02
(Incorporate Amendment 05) | 27-Jun-2017   | 
 
1. Increase in the size of the platinum eligible population in order to provide greater estimation precision.
 
2. Alignment of protocol with responses to regulatory authorities.
 
3. Minor changes to eligible criteria and study processes.
 
4. Clarification of outstanding issues and correction of typographical errors.
 
   |
| Revised Protocol 03                               | 14-Nov-2017   | 
Correct mistakes introduced by Revised Protocol 02 and add a potential interim analysis.
   |
| Revised Protocol 04                               | 16-May-2018   | 
 
1. Incorporate Administrative letter (change in study personnel)
 
2. 
 
3. Clarify timing of the planned interim analysis and final analysis and update statistical analysis plan
 
4. Other minor edits and clarifications.
 
  |

## **2.5 Data monitoring Committee**

A Data Monitoring Committee (DMC) will be utilized to provide general oversight and safety considerations for this study. The DMC will provide advice to the Sponsor regarding actions the committee deems necessary for the continuing protection of subjects treated in this study. The DMC will be charged with assessing such actions in light of an acceptable risk/benefit/ profile for nivolumab in combination with placebo, and nivolumab in combination with ipilimumab. The DMC will act in an advisory capacity to BMS and will monitor subject safety data for the study approximately every 6 months for the duration of the trial.

The DMC will be advisory to the clinical study leadership team. The clinical study leadership will have responsibility for overall conduct of the study including managing the communication of study data. The group will be responsible for promptly reviewing the DMC recommendations, for providing guidance regarding the continuation or termination of the study, and for determining whether amendments to the protocol or changes to the study conduct are required.

## **3 OBJECTIVES**

### **3.1 Primary**

To compare the ORR and assess DOR of the treatment of nivolumab in combination with ipilimumab vs. nivolumab in combination with ipilimumab placebo, as determined by a blinded independent central review (BICR) using RECIST 1.1 criteria, for first line treatment of recurrent or metastatic SCCHN in the platinum refractory setting.

### **3.2 Secondary**

- To estimate the ORR and assess DOR of the treatment of nivolumab in combination with ipilimumab vs nivolumab in combination with ipilimumab placebo, as determined by BICR using RECIST 1.1 criteria, for first line treatment of recurrent or metastatic SCCHN in the platinum eligible setting
- To assess progression-free survival (PFS), as determined by BICR, of nivolumab in combination with ipilimumab vs. nivolumab in combination with ipilimumab placebo for first line treatment of recurrent or metastatic SCCHN in the platinum eligible and platinum refractory settings, separately and overall
- To assess overall survival (OS), of nivolumab in combination with ipilimumab vs. nivolumab in combination with ipilimumab placebo for first line treatment of recurrent or metastatic SCCHN in the platinum eligible and platinum refractory settings, separately and overall
- To assess efficacy (ORR, DOR, PFS and OS) by PD-L1 expression of nivolumab in combination with ipilimumab compared to nivolumab in combination with ipilimumab placebo for first line treatment of recurrent or metastatic SCCHN in the platinum eligible and platinum refractory settings, separately and overall
- To assess efficacy (ORR, DOR, PFS and OS) by HPV p-16 status of nivolumab in combination with ipilimumab compared to nivolumab in combination with ipilimumab placebo for first line treatment of recurrent or metastatic SCCHN in the platinum eligible and platinum refractory settings, separately and overall

- To evaluate tumor mutation burden, as a potential predictive biomarker of efficacy (such as ORR, DOR, PFS and OS) of nivolumab in combination with ipilimumab or ipilimumab placebo for first-line treatment of recurrent or metastatic SCCHN in the platinum eligible and platinum refractory settings, separately and overall.

[REDACTED]

## 4 ENDPOINTS

### 4.1 Primary Endpoint

#### 4.1.1 *Objective Response Rate by BICR and Duration of Objective Response in Platinum Refractory Subgroup*

Objective response rate by BICR and Duration of Objective Response (DOR) in the platinum refractory subgroup are the primary endpoints of this study. ORR is defined as the number of randomized subjects with a best overall response (BOR) of a complete response (CR) or partial

response (PR), assessed by BICR per RECIST 1.1, divided by the number of randomized subjects for each treatment group. Note that to achieve a best response of CR or PR, confirmation is required.

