### **1.4 Research Hypothesis**

- In patients with recurrent or metastatic SCCHN, the administration of nivolumab in combination with ipilimumab as first-line therapy in the platinum refractory setting will improve objective response rate (ORR) and duration of response (DOR) compared to nivolumab in combination with ipilimumab placebo.

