## 5 SAMPLE SIZE AND POWER

The primary objective is to compare the ORR of nivolumab in combination with ipilimumab vs nivolumab in combination with ipilimumab placebo, as determined by BICR using Response Evaluation Criteria In Solid Tumors (RECIST 1.1) criteria in platinum refractory subjects with recurrent or metastatic SCCHN. The alpha level for the ORR is adjusted for one planned interim analysis using Lan-DeMets alpha spending function with O’Brien-Fleming boundaries, which will be determined by the fraction of subjects included in the interim analysis. Given that the interim analysis for the primary endpoint is expected to be performed when 70% of platinum refractory subjects have reached 6 months follow up after randomization, the alpha level is expected to be 0.015 for the interim analysis and 0.045 for the final analysis.

Approximately 396 subjects (216 platinum refractory subjects and 180 platinum eligible subjects) will be randomized to either nivolumab plus ipilimumab or nivolumab in combination with ipilimumab placebo in a 2:1 ratio.

A sample size of 216 randomized platinum refractory subjects (144 and 72 respectively) will provide 84% power for testing the odds ratio of nivolumab plus ipilimumab over Nivolumab in combination with placebo, with a 0.050 two-sided significance level, assuming ORR of 35% and 15% (odds ratio of 3.051) in the nivolumab plus ipilimumab and nivolumab in combination with ipilimumab placebo treatment group respectively (odds ratio of proportions test using EAST v6).

Only the primary endpoint will be tested, none of the secondary endpoints.

The first secondary objective is to estimate the ORR of the treatment of nivolumab in combination with ipilimumab vs nivolumab in combination with ipilimumab placebo, as determined by BICR using RECIST 1.1 criteria for first line treatment of recurrent or metastatic SCCHN in the platinum eligible setting.

Approximately 180 subjects (120 and 60 respectively) will be randomized in the platinum eligible subgroup. For a sample size of 120 subjects randomized to nivolumab plus ipilimumab, the maximum width of the exact two-sided 95% confidence interval (CI) is 18.6% when the ORR is expected to be in the 10% to 55% range. The table below summarizes the 95% exact CI when observed ORRs are between 10% and 55% respectively.

Table 5-1: Observed ORR with Exact 95% CI in Platinum Eligible Subjects randomized to nivolumab plus ipilimumab (N=120).

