## **7 STATISTICAL ANALYSES**

### **7.1 General Methods**

Unless otherwise noted, the bulleted titles in the following subsections describe tabulations of discrete variables, by the frequency and proportion of subjects falling into each category, grouped by treatment (with total). Percentages given in these tables will be rounded and, therefore, may not always sum to 100%. Continuous variables will be summarized by treatment group (with total) using descriptive statistics; ie, number of non-missing observations (n), mean, standard deviation (STD), median, minimum, maximum and quartiles. If a missing category is not being presented in the data display, only those subjects with non-missing values for the parameter being assessed are included in the percentage calculation.

Time to event distributions (i.e. progression free survival, overall survival, time to response, and duration of response) will be estimated using the Kaplan-Meier product limit method. When appropriate, estimates of the median time to event will be presented, along with associated 95% CIs. The confidence interval for the median will be obtained based on the log{-log} transformation of the survival function. Kaplan-Meier estimates of rates at fixed time points (e.g. OS at 12 months) will be presented along with 95% confidence intervals for those rates. The confidence interval for the rate at time  $t_0$ ,  $S(t_0)$ , will be obtained by first computing the interval for  $\log(-\log(S(t_0)))$  and then back transforming. (The methods specified above for computing the confidence intervals for median time to event and for survival rates are the default methods in SAS.)

Unless otherwise specified, the hazard ratio of Nivolumab plus ipilimumab to Nivolumab plus ipilimumab placebo, and its associated CI, will be obtained by fitting a stratified Cox model with the treatment group variable as the sole covariate using stratification factor recorded in the IVRS.

Confidence intervals for binomial proportions will be derived using the Clopper-Pearson method.

P-values from sensitivity analyses for efficacy endpoints are for descriptive purpose only and there will be no multiplicity adjustment for these analyses.

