### **7.5 Efficacy**

Unless otherwise specified, efficacy analyses will be performed for all randomized subjects by treatment group as randomized, overall and for platinum refractory and platinum eligible subgroups separately.

CI's for efficacy endpoints will be at the two-sided 95% level, except for the primary endpoint ORR for platinum-refractory subjects where CI is anticipated to be provided at 98.5% level for the interim and 95.5% level for the final analysis (see [Section 7.5.1](#)). The p-values presented in the clinical study report will be rounded to the fourth decimal place. Point estimates and confidence intervals for efficacy variables will be rounded to the second decimal place. P-value will only be provided for the comparison of ORR between nivolumab in combination with ipilimumab vs nivolumab in combination with ipilimumab placebo in platinum refractory randomized subjects.

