### 7.5.1 Primary Endpoint ORR in Platinum Refractory Subgroup

The primary endpoint of the study is ORR in platinum refractory subgroup, as determined by a blinded independent central review (BICR) using RECIST 1.1 criteria.

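### SAP 2.1 allows the primary ORR analysis at 6 months' minimum follow-up where the protocol requires 9, and SAP 4.1.1 labels DOR a primary endpoint although only ORR is powered and tested

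*SAP*

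**What the plan says.** **Timing.** SAP 2.1 places the primary ORR analysis of each platinum subgroup after its last randomized subject has at least 6 months' follow-up. Protocol 8.3.1 places the final analysis of the primary endpoint at least 9 months after the last platinum refractory subject is randomized. The synopsis (Study Design) and protocol 3.2 and 8.3.2 also give 9 months. SAP 2.4 says that SAP version 3.0 incorporates Revised Protocol 04, whose stated purposes include clarifying when the interim and final analyses take place.

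**Role of DOR.** SAP 4.1.1 says "Objective response rate by BICR and Duration of Objective Response (DOR) in the platinum refractory subgroup are the primary endpoints of this study". Protocol 1.4 hypothesises that the combination "will improve objective response rate (ORR) and duration of response (DOR) compared to nivolumab in combination with ipilimumab placebo". Against this:

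- Protocol 8.3.1: "The primary objective in the study will be measured by the primary endpoint of ORR in Platinum Refractory subgroup". The same section uses DOR and time to response to characterise ORR further.
- SAP 7.5.1: "The primary endpoint of the study is ORR in platinum refractory subgroup". Protocol 5.4.1 agrees.
- SAP 3.1 (and protocol 1.5.1): "To compare the ORR and assess DOR of the treatment of nivolumab in combination with ipilimumab".
- SAP 5: "Only the primary endpoint will be tested, none of the secondary endpoints".
- SAP 7.5, on the platinum refractory subgroup: "P-value will only be provided for the comparison of ORR between nivolumab in combination with ipilimumab vs nivolumab in combination with ipilimumab placebo".

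SAP 7.5.1.4 plans Kaplan-Meier curves, a median with 95% CI, the range, and the proportion of responses lasting at least 6 months. All are by arm among responders.

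**The concern.** SAP 2.1 is the only visible place in the SAP that dates the final ORR analysis. A team working from it could lock data up to 3 months earlier than the protocol permits and believe that it had followed the plan. The primary result would then rest on a cut that breaches the protocol, and the durability summaries would be less mature than the protocol intends.

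The DOR label matters less, but it does touch a rule. If DOR is a primary endpoint (SAP 4.1.1) and the primary endpoint is what gets tested (SAP 5), DOR should be tested. SAP 7.5 gives it no p-value, and nothing in the plan gives it alpha, power or a precision target. Together with a hypothesis that DOR improves, the label invites a report to present DOR as a primary result with no planned inference behind it.

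**Working it through.** **1. Timing statements side by side**

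| Place | Minimum follow-up | Counted for |
|---|---|---|
| Protocol synopsis, 3.2 | 9 months | a sufficient number of randomized subjects in each subgroup |
| Protocol 8.3.1 | 9 months | the last platinum refractory subject randomized |
| Protocol 8.3.2 | 9 months | once about 216 (refractory) or 180 (eligible) are randomized |
| SAP 2.1 | 6 months | the last randomized subject in the subgroup |
| SAP 7.5.1.1, 7.5.6 (interim) | 6 months | around 70% of platinum refractory subjects |

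The interim rule concerns about 0.70 × 216 = 151 subjects. SAP 2.1 speaks of the last subject and of the primary analysis, so its 6 months is not the interim rule restated.

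**2. What a 6-month cut leaves out**

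- The first scan is at week 6 ± 1 week (protocol 5.4.1), so the earliest is week 5: 35 / 30.4375 = 1.15 months from first dose.
- A response first seen then reaches 6 months at 1.15 + 6 = 7.15 months. This is a lower bound, because later first responses take longer.
- Protocol 3.2 gives about 13 months' accrual. Assume that this applies to the refractory subgroup and is uniform. A cut 6 months after the last randomization gives 6 to 19 months' follow-up.
- Share with at least 7.15 months: (19 − 7.15) / 13 = 91%. Share without: 1.15 / 13 = 8.8%, or 0.088 × 216 ≈ 19 subjects.
- Other accrual periods (assumed): over 10 months, 1.15 / 10 = 11.5% (about 25 subjects); over 20 months, 1.15 / 20 = 5.8% (about 12).
- At a 9-month cut every subject is past 7.15 months.

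The small gap between randomization and first dose is ignored. It would only lengthen the time needed.

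**3. Which endpoint the stated power and alpha belong to**

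Inputs from protocol 8.1 and SAP 5: 144 v 72 subjects, ORR 35% v 15%, odds ratio 3.051, two-sided 0.05, stated power 84%.

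- log(3.051) = 1.116
- SE = √[1/(144 × 0.35 × 0.65) + 1/(72 × 0.15 × 0.85)] = √(0.0305 + 0.1089) = 0.373
- z = 1.116 / 0.373 = 2.99
- Power at 0.05: Φ(2.99 − 1.96) = 84.8%. At the final level 0.045: 83.7%.

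The Lan-DeMets O'Brien-Fleming function at 70% information, spent separately in each tail, gives 0.0148 at the interim. With an interim level of 0.015, the final level is 0.0454. These match the stated 0.015 and 0.045. The power and the whole of the alpha therefore come from ORR alone, and none is set aside for DOR.

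**4. How much DOR information to expect**

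- Expected responders: 144 × 0.35 = 50.4 and 72 × 0.15 = 10.8 (binomial 95% ranges 39–62 and 5–17).
- As an illustration, suppose about 60–65% of control responses last 6 months. The exact 95% CI is 31–89% for 7/11, 15–95% for 3/5 and 38–86% for 11/17, before any censoring.

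**The case against.** **On timing.** Both documents state minimums, so a cut at 9 months or later satisfies both. SAP 2.1 is a study description that also omits the 24-month treatment limit given in protocol 3.2. Most subjects would have ample follow-up even at 6 months, and Kaplan-Meier methods handle the rest by censoring. All of this is fair and limits the size of the problem. It does not remove the conflict, because no other visible passage in the SAP corrects the figure.

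**On DOR.** The operative text already settles testing. The objective compares ORR and only assesses DOR, protocol 8.3.1 gives DOR a characterising role, and SAP 7.5 confines the p-value to ORR. This stands, and it makes the label a minor point.

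**Stronger readings that a reader might infer:**

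- *That the SAP calls for a DOR hazard ratio.* SAP 7.1 says "Time to event distributions (i.e. progression free survival, overall survival, time to response, and duration of response) will be estimated" and then describes how a hazard ratio is obtained unless otherwise specified. That gives a method; it does not request a hazard ratio for every listed variable. The same list includes time to response, which gets only summary statistics in SAP 7.5.1.5. Hazard ratios are requested explicitly for PFS and OS (SAP 7.5.3.1, 7.5.4.1), and SAP 7.5.6 gives DOR a Kaplan-Meier estimate and median only.
- *That every between-arm statement on DOR should be barred.* The secondary objectives assess efficacy, DOR included, by PD-L1 and HPV p-16 status for the combination compared with control. Protocol 8.3.2 and SAP 4.2.1 also make DOR a secondary endpoint in the platinum eligible subgroup. A blanket ban would conflict with these.

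SAP 7.5.1.6 and 7.5.1.7 and protocol 8.4.2.2 are not visible in the public copy, so statements about planned DOR analyses cover the visible text only.

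**Conclusion.** The timing statement in SAP 2.1 is wrong as written: it permits a primary data cut that the governing protocol does not. The exposure is confined to a cut between 6 and 9 months. At a 6-month cut, about 9% of the subgroup (6–12% for accrual over 20 to 10 months, assumed uniform) could contribute to the 6-month DOR proportion only as censored or as already ended.

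The endpoint label is a minor inconsistency. A reader might infer an untested co-primary endpoint or inflated type I error. The documents support neither, because ORR carries all the alpha, the 84% power reproduces from ORR inputs alone, and only ORR receives a p-value. What remains is a label and a hypothesis that promise more on DOR than the plan delivers. A contrast of about 50 v 11 responders, a group formed after randomization, could not support a formal claim. That count assumes the design response rates.

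**What to change.** 1. **SAP 2.1:** change the minimum follow-up for the primary ORR analysis from 6 to 9 months, in line with protocol 8.3.1 and 8.3.2. The interim rule in SAP 7.5.1.1 and 7.5.6 stays as it is.
2. **SAP 4.1.1:** name ORR by BICR in the platinum refractory subgroup as the sole primary endpoint, with DOR characterising it further as in protocol 8.3.1. The primary objective can stand, since it only assesses DOR.
3. **SAP 7.5.1.4:** state that DOR in the platinum refractory subgroup is descriptive, by arm among responders, and is not formally tested.
4. **Protocol 1.4 and synopsis hypothesis:** limit the hypothesis to ORR at the next amendment.

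Items 1 to 3 are SAP wording, best settled before database lock. Item 4 needs IRB/IEC review under protocol 9.1.1, so it should travel with an amendment made for other reasons. No analysis is added, and the sample size, ORR test, alpha and power do not change. The one loss is that DOR gives up the primary label.
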